5.8.3 Dispensing of Study Drug

A prescription will be written, signed by an Investigator and faxed to the Research Pharmacy for the baseline and 3 month visit dispensing. The subject/LAR will either pick up the medication at the Out-Patient Pharmacy or if picked up in advance by a study team member, will be provided to the subject by the study team with a dosing/AE diary.

5.8.4 Return or Destruction of Study Drug

At the completion of the study, there will be a final reconciliation of drug amounts shipped, dispensed, returned, and remaining. This reconciliation will be included in study files. Any discrepancies noted will be documented and investigated, prior to return or destruction of unused study drug. Any investigational drug destroyed on site according to institutional waste policy will be documented by the Research Pharmacy.

6 Study Procedures

The schedule of events for patients enrolled in this trial is shown in Attachment II. See Section 3 for visit descriptions.

7 Statistical Plan

Statistical analysis will be performed using SAS version 9.3 (SAS Inc., Cary, NC). All tests will be two sided and p-values less than 0.05 will be considered statistically significant.

7.1 Sample Size Determination

A recent single-center open-label pilot study enrolled eight adults with genetically-confirmed Becker muscular dystrophy, who received 100 mg/day of EPI orally for 8 weeks. The data showed linear decrease in plasma B-Type Natriuretic Peptide (BNP) levels, a validated biomarker of congestive heart failure [15]. Assuming a common standard deviation of 234.3 as seen in the Becker pilot study, with a sample size of 10 patients we should have 80% power to detect an effect size (on BNP and possibly other biomarkers) of 1 at a 5% level of significance based on a paired t-test. NQuery Advisor version 6.0 was used for sample size calculations.

7.2 Statistical Methods

Descriptive Statistics

All numerical data will be imported into a dedicated application of highly-innovative multivariate pattern recognition software developed at Mayo by [REDACTED] that provides an integrated analysis of outcome measures after statistical adjustment for one or more relevant covariates. Descriptive summaries will be reported as frequencies and percentages for categorical variables and as mean (standard deviation) or median (inter-quartile range) for continuous variables of interest.

Handling of Missing Data

Data edit checks will be performed to assess outliers or any inconsistencies done at the time of data entry. No imputations will be performed for any missing data.

Multiplicity

Given the smaller sample size, no formal adjustment for multiple comparisons will be performed. We will however, report both raw (unadjusted) and false discovery rate corrected p-values.

Primary Hypothesis:

In light of the common underlying pathogenic mechanism of energy deficit and oxidative damage, we hypothesize that the induction of mitochondrial biogenesis and bioenergetics along with simultaneous upregulation of the cellular antioxidant defenses is a strategy capable to ameliorate MtD. To test this hypothesis we propose to conduct a phase II drug clinical trial to test the efficacy of a novel synthetically-produced form of Epicatechin (EPI) in patients with Friedreich's Ataxia (FA). For continuous endpoints such as FARS assessment, we will calculate changes from baseline to 12 weeks and 24 weeks. These will be summarized and mean (standard deviation) or median (inter-quartile range). We will also report 95% confidence intervals. Formal comparison to assess

efficacy of intervention will be performed using paired t-test or Wilcoxon signed rank test as appropriate. Analysis will also be performed using percent changes from baseline to 12 week and 24 week to account for baseline discrepancies. Data will be displayed graphically using scatter plots to show the trends over time. Categorical outcomes will be compared using McNemar's test as a test of paired proportions to account for paired nature of the data.

Secondary Hypothesis 1:

- Upregulate mitochondrial biogenesis via activation of the transcription factor PGC-1 α [9] which is downregulated in FA [45]; this may lead to higher levels of frataxin as well as higher levels of Fe-S proteins critical for ATP production.
- Upregulate endogenous antioxidant mechanisms (SOD2, catalase) controlled by the Nrf2 pathway [18] which is inhibited in FA cells [46]; this may enhance FA cells resistance to iron-catalyzed oxidative damage.
- Promote fatty acid oxidation through regulation of SIRT3 signaling [9, 19] which is inhibited in FA cardiac cells and believed to contribute to the FA cardiomyopathy [47].
- Enhance insulin sensitivity through the PI3K/AKT pathway and AMPK [10] which may further improve metabolic dysfunction in FA.
- Through the basic mechanisms described above, (+)-EPI treatment will ultimately prevent further loss of neuronal, cardiac, and pancreatic β cells and thereby delay or arrest FA neurodegeneration, cardiomyopathy and diabetes.

Statistical analysis approach for secondary endpoint will be similar to approach listed above for primary endpoints.

Interim Analysis

Interim analysis will be performed after 50% i.e. 5 out of 10 patients have completed 12 week follow-up. Sample size at interim analysis is too small to reach required p-value for stopping decision based on O'Brien Fleming Stopping boundary criterion (i.e. p-value less than 0.0054 for stopping at interim analysis). Thus decision of stopping versus continuation of the study will be based on clinical significance rather than statistical significance. We will consider treatment to be efficacious if the cardiac MRI, neurologic MRI, and /or FARS score improve by greater than 30% at 3 months.

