ST2	Suppressor of tumorigenicity 2
TID	Ter in die (three times a day)

Study Summary

Title	A Phase II, Open Label Prospective Single Center Drug Study Evaluating the Safety and Efficacy of (+)-Epicatechin in Subjects with Friedreich’s Ataxia
Running Title	Safety and Efficacy of (+)-Epicatechin in Friedreich’s Ataxia
Protocol Number	15-006845
Phase	Phase II
Methodology	This is an open label, single center, prospective phase II drug trial to assess the safety and efficacy of (+)-EPI in the treatment of Friedreich’s Ataxia. Subjects will be evaluated at outpatient clinic visit appointments and interested qualified subjects will be consented and offered participation in this trial. Once consent has been obtained, baseline values will be established and subjects will begin treatment and follow-up over a 24 week period. Clinical and biochemical parameters will be assessed at baseline and at 12 and 24 weeks after initiation of treatment.
Overall Study Duration	Two years estimated to complete enrollment
Subject Participation Duration	24 weeks
Single or Multi-Site	Single center
Objectives	
Primary: To assess the safety and clinical efficacy from neurological, cardiac and metabolic evaluations of patients before and after treatment.
 
Secondary: To assess (i) up-regulation of relevant mitochondrial proteins (frataxin and ETC complexes I-V) and (ii) reduction of urine F2-isoprostane, before and after treatment.
 
Exploratory: To assess myocardial oxygenation by Blood Oxygenation Level Dependent (BOLD) sequence cardiac MRI, and myocardial perfusion index by Regadenoson-stress-perfusion cardiac MRI, before and after treatment as non-invasive, more sensitive endpoints for future studies.
 
To investigate neuroimaging biomarkers of disease progression including spinal cord and cerebellar volumetry, Diffusion Tensor Imaging (DTI), and Magnetic Resonance Spectroscopy (MRS).

Number of Subjects	10 subjects

Diagnosis and Main Inclusion Criteria	Study participants between the ages of ≥ 10 and ≤ 50 must have a confirmed diagnosis of Friedreich's Ataxia with disease duration ≤ 7 years and at least one affected organ system (cardiac or neurological)
Study Product, Dose, Route, Regimen	(+)-Epicatechin 25mg capsules will be administered orally TID for 24 weeks, with dose escalation to 50mg TID at 3 months for subjects not showing improvement.
Duration of Administration	24 weeks
Reference therapy	No reference therapy

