3.2 Primary Study Endpoints

Neurological:

- Change from baseline score using Friedreich's Ataxia Rating Scale (FARS Assessment) tool at 12 and 24 weeks.
- Changes in spinal cord fractional anisotropy, based on axial DTI measurements prescribed at the C1, T1, and L1 levels at 24 weeks.

Cardiac:

- Changes in Cardiac MRI from baseline to 12 and 24 weeks:
 - Left ventricular structural and functional characteristics (systolic function by ejection fraction and systolic strain, diastolic function, LV mass to determine ventricular hypertrophy and degree of heart failure, myocardial fibrosis by late gadolinium enhancement).
- Changes in Echocardiogram from baseline to 24 weeks:
 - Left ventricular mass, volumes, systolic and diastolic function, and strain.
- Changes in Electrocardiogram from baseline to 24 weeks to assess for electrophysiological improvement of the myocardium.
- Changes in biomarkers for heart failure and hypertrophy (ST2, BNP, Cardiac Troponin) from baseline, at 12 weeks and 24 weeks.

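### For positive, right-skewed biomarkers, the supplementary percent-change analysis has an upward-biased mean and a lopsided t-test; a log ratio keeps the own-baseline scaling without either

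*Combined protocol and SAP*

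**What the plan says.** Section 7.2 sets the main analysis first. Continuous endpoints, with FARS as the example, are analysed as change from baseline to weeks 12 and 24, summarised by mean or median with 95% confidence intervals. The formal comparison to assess "efficacy of intervention will be performed using paired t-test or Wilcoxon signed rank test as appropriate". One sentence later the plan adds a further analysis, using "percent changes from baseline to 12 week and 24 week to account for baseline discrepancies". It does not say which endpoints this applies to, or which result prevails if the two analyses disagree. Secondary endpoints get a similar approach. No log or ratio analysis is named.

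The opening of Section 7 states: "All tests will be two sided and p-values less than 0.05 will be considered statistically significant". The Study Summary gives "No reference therapy", so there is one arm.

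The blood markers are not marginal to the plan. Section 3.2 lists among the primary endpoints "Changes in biomarkers for heart failure and hypertrophy (ST2, BNP, Cardiac Troponin) from baseline, at 12 weeks and 24 weeks", and Section 7.1 bases the sample size on BNP. Section 3.3 adds F2-isoprostane (expected to fall) and frataxin and the ETC complexes (expected to rise) as secondary endpoints.

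**The concern.** With one arm there is no between-group imbalance to correct, so the only sensible meaning of the rationale is that patients start at different levels. Percent change does address that, but for a noisy positive marker it does so asymmetrically. A chance low baseline can produce a very large percent rise, while no fall can exceed 100%. The mean percent change is therefore above zero when nothing has happened.

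The consequence depends on direction. Where benefit is a fall (BNP, F2-isoprostane), the asymmetry works against finding it and shrinks the mean effect. Where benefit is a rise (frataxin, ETC complexes), it works in the drug's favour. In a 10-patient trial with many biomarkers, this analysis could weaken the most plausible signals in one direction and favour chance findings in the other.

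**Working it through.** **The plan's own figure.** Section 7.1 states that "with a sample size of 10 patients we should have 80% power to detect an effect size" of 1 in a two-sided 5% paired t-test. Noncentral t with 9 degrees of freedom and noncentrality 1 × √10 = 3.16 gives 80.3%. The stated 80% reproduces. The planning SD of 234.3 cancels because the effect is in SD units.

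**Inputs.** n = 10, two-sided alpha 0.05 and one arm come from the documents. The within-subject CV of a single measurement is assumed at 20% to 50%, because the documents give no within-patient variability for any endpoint. A true 30% fall is an illustrative effect.

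**Model.** Baseline is exp(b + e0) and follow-up is r × exp(b + e1). Here b is the patient's own level, r the true ratio, and e0 and e1 are independent normal errors with variance ln(1 + CV²). The level b cancels in the ratio. The log ratio has mean ln r and SD s, with s² = 2 ln(1 + CV²).

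**Bias of the mean.** The mean ratio is r × exp(s²/2) = r × (1 + CV²), so mean percent change = r(1 + CV²) − 1.

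- No effect (r = 1): +4%, +9%, +16% and +25% at CV 20%, 30%, 40% and 50%.
- True 30% fall (r = 0.7) at CV 40%: 0.7 × 1.16 − 1 = −0.188, which is about −19% instead of −30%.

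**False positives.** Simulated trials of 10 patients with no effect at CV 40%: the percent-change t-test declares an increase in about 3.6% of trials and a decrease in about 1.6%. The log-ratio test gives 2.5% each way.

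**Power for a 30% fall.** For the log ratio, the standardised effect is |ln 0.7| / s. At CV 30% this is 0.357/0.415 = 0.86, giving 68%. At CV 40% it is 0.357/0.545 = 0.65, giving 46%. Percent-change power is simulated.

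| CV | Percent change | Log ratio |
|---|---|---|
| 20% | 91% | 95% |
| 30% | 57% | 68% |
| 40% | 34% | 46% |

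**Power for a rise of the same log size (r = 1/0.7).** Here percent change is slightly ahead: about 72% against 68% at CV 30%, 51% against 46% at CV 40%, and 38% against 33% at CV 50%.

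**Against the plan's absolute change.** With an assumed between-patient log SD of 0.8 and a 30% fall, percent change beats absolute change by t-test: 57% against 43% at CV 30%, and 34% against 27% at CV 40%.

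**FARS-like data.** With additive normal data (assumed mean 30 to 50, visit SD 2 to 5), the bias under no effect is only +0.3% to +1.4%. At a 1-SD effect, percent change has 71% to 79% power and log ratio 71% to 78%. Both are at or below absolute change at 80%.

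**The case against.** Several points on the other side stand.

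- **The analysis is supplementary.** Section 7.2 says it is done in addition. The main paired test on absolute change and the power statement do not depend on it.
- **It does useful scaling.** A reader might infer that percent change adjusts for nothing in a single-arm trial. That goes too far: with widely spread baselines and proportional effects it beats the plan's own absolute-change t-test, as shown above. It does not remove regression to the mean, but neither does a log ratio.
- **The power loss is not general.** It applies to falls. For moderate rises percent change is a little ahead, though that advantage comes with the same upward bias. For FARS-like data it is level with the log ratio.
- **The bias is in the mean.** Section 7.2 also allows a median. In the simulations the median percent change was 0% under no effect and −30% for a true 30% fall. The Wilcoxon test, however, does not restore power for falls: at s = 0.28 with a shift of 1 SD of the log ratio it has 71% for percent change against 79% for log ratio.
- **Every CV is assumed.** At CV 20% the difference is small.
- **The log ratio has limits too.** It fails if either visit is zero, whereas percent change fails only at a zero baseline.

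A reader might also infer that overall type I error is inflated, or that the interim 30% improvement criterion is distorted. Neither is shown. Two-sided error stays near 5%. The interim criterion concerns MRI and FARS, and the bias for FARS-like data is at most +1.4% under the assumptions used.

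**Conclusion.** The point holds for positive, right-skewed blood and urine markers and is minor. Under log-normal within-subject variation with assumed CVs of 20% to 50%, the mean percent change is +4% to +25% when nothing has changed, and the false-positive rate tilts upward. For a 30% fall with 10 patients, about 11 to 12 percentage points of power are lost against a log ratio at CV 30% to 40%, and about 4 points at CV 20%. For markers expected to rise, the tilt is towards a false finding of benefit.

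The documents do not support the stronger conclusion that the trial's main efficacy result is biased or underpowered because of this analysis. The point is still worth acting on because BNP is the sample-size marker, BNP, ST2 and troponin are listed as primary endpoints, and a method exists that keeps what percent change is meant to achieve.

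**What to change.** In Section 7.2, fix the scale by type of endpoint:

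- For strictly positive blood and urine biomarkers, replace the percent-change analysis with the paired test on log(follow-up/baseline), reported as a geometric mean ratio with 95% CI.
- Keep absolute change for FARS, imaging and any endpoint that can be zero or negative.
- Reword the rationale as scaling each change to the patient's own baseline.
- State one fixed convention for values below the assay limit, and say that it is separate from the rule against imputing missing data.

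The cost is a change of wording, with no new data, patients or visits. The downsides are the need for that assay-limit convention and a slight loss of power for moderate rises (68% against about 72% at CV 30%).

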4.5 Replacement of Discontinued or Withdrawn Subjects

Subjects who discontinue or are withdrawn prior to completing twenty-four (24) weeks of treatment will be replaced, to achieve a target of ten subjects completing 24 weeks of dosing with study medication. The number replaced may be limited to the available inventory of (+) Epicatechin capsules.

5 Study Drug

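### Section 7.2 permits an efficacy stop on 12-week data from five subjects, which would miss the ten-completer target and leave the week-24 primary endpoints on fewer subjects

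*Combined protocol and SAP*

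**What the plan says.** Section 7.2 (Interim Analysis) fixes the timing: "Interim analysis will be performed after 50% i.e. 5 out of 10 patients have completed 12 week follow-up". It names an O'Brien-Fleming boundary ("i.e. p-value less than 0.0054 for stopping at interim analysis") and says that the interim sample is too small to reach it. It continues: "Thus decision of stopping versus continuation of the study will be based on clinical significance rather than statistical significance". The next sentence supplies the only criterion: "We will consider treatment to be efficacious if the cardiac MRI, neurologic MRI, and /or FARS score improve by greater than 30% at 3 months".

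Other sections set what the trial is meant to deliver:

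- Section 4.5 replaces subjects who leave early, "to achieve a target of ten subjects completing 24 weeks of dosing with study medication", subject to capsule inventory.
- Section 3.2 lists primary endpoints due only at week 24: spinal cord fractional anisotropy, echocardiogram and ECG (for example "Changes in Electrocardiogram from baseline to 24 weeks to assess for electrophysiological improvement of the myocardium"). Attachment II agrees, with neurological imaging, echocardiogram and ECG at weeks 0 and 24 only. FARS, cardiac MRI and the heart-failure biomarkers are primary at both week 12 and week 24.
- Section 7.1 bases the sample size on ten subjects: "with a sample size of 10 patients we should have 80% power to detect an effect size". The effect in question is 1 SD, set mainly for BNP, and the test is a paired t-test at the 5% level.
- Section 8.4 holds the halting rules, and these concern safety only. Section 4.4.1 lists what ends the trial for a patient, and an early stop of the study is not on the list.

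**The concern.** The stop-or-continue decision uses half the planned subjects at half the planned follow-up, and no error rate is attached to the 30% criterion that replaces the boundary. Acting on it would give up data that other sections require: ten completers, and primary endpoints that do not exist at week 12. Dose escalation under Section 3.1 also begins only at the week-12 visit, so the data driving the decision contain no exposure to the escalated dose.

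The usual reason for an efficacy stop is to avoid keeping control patients off an effective treatment. That reason is absent here, because every enrolled subject receives the drug. The stop would only remove information from a trial of ten.

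The plan also leaves the consequence undefined. Stopping might close enrolment while enrolled subjects complete week 24, or it might end their assessments as well. Section 7.2 imputes nothing, so any week-24 assessment not made is simply missing.

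**Working it through.** **Inputs.** n = 10, effect size 1 SD, paired t-test, 5% level (Section 7.1), two-sided (opening of Section 7). Interim at 5 subjects with week-12 data (Section 7.2). Accrual: the Study Summary gives two years to complete enrolment. Section 3.1 gives about two years including the final assessment, so 104 − 24 = 80 weeks of accrual, or about 18 months.

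**Step 1: reproduce the plan's power.** Power is P(|T| > t(0.975, n−1)), where T is noncentral t with n−1 degrees of freedom and noncentrality d√n. For n = 10 and d = 1 the critical value is 2.262 and the noncentrality 3.162, giving 80.3%. The stated 80% reproduces.

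**Step 2: where subjects stand at the interim.** Assume ten evenly spaced entries, the first at week 0 and the tenth at the end of accrual, with no dropout. The interim falls 12 weeks after the fifth entry.

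- 104 weeks: spacing 104/9 = 11.6 weeks, fifth entry at week 46.2, interim at week 58.2. The sixth entry is at week 57.8, so 6 are enrolled. Subjects who entered by week 34.2 have reached week 24: those at 0, 11.6 and 23.1, so 3.
- 80 weeks: spacing 80/9 = 8.9 weeks, fifth entry at week 35.6, interim at week 47.6. Again 6 are enrolled and 3 have reached week 24.
- Faster accrual, by the same count: over 12 months, 7 enrolled and 2 at week 24; over 6 months, 9 enrolled and 0 at week 24.

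**Step 3: what each outcome leaves.** The 95% CI half-width for a mean change is t(0.975, n−1)/√n, in SD units. The exact upper 95% limit for an event seen in none of n is 1 − 0.025^(1/n).

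| Situation | n | Power at 1 SD | CI half-width | Upper limit, 0/n |
|---|---|---|---|---|
| Planned, week 24 | 10 | 80% | 2.262/√10 = 0.72 SD | 31% |
| Stop closes enrolment, 6 followed to week 24 | 6 | 51% | 2.571/√6 = 1.05 SD | 46% |
| Interim comparison itself, week 12 | 5 | 40% | 2.776/√5 = 1.24 SD | not used |
| Stop also ends follow-up, week-24 data | 3 | 18% | 4.303/√3 = 2.48 SD | not used |

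The event limit is shown only for 10 and 6, because safety counts everyone dosed and not only those with an efficacy assessment.

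**Step 4: compare with the target.** Under 18- to 24-month accrual a stop leaves at most 6 completers of the 10 that Section 4.5 seeks, and about 3 if follow-up ends too.

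**The case against.** A reader might infer that under this rule the week-24 endpoints and the ten-completer target would never be reached. The documents do not support that.

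- Section 7.2 never says outright that meeting the 30% criterion means stopping. It says that treatment will be considered efficacious.
- No section ends follow-up of enrolled subjects, and Section 4.4.1 does not list an early study stop as a patient's end of trial.
- FARS, cardiac MRI and the heart-failure biomarkers are primary at week 12 too. BNP, on which the power statement rests, is one of them.
- About 3 subjects would already have week-24 data under the assumed accrual.

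A reader might also apply n = 5, and so 40% power, to the whole trial. That figure belongs to the interim comparison only. If enrolled subjects finish, the week-24 number is about 6 and power is 51%. Nor can the loss of information at the escalated dose be sized: escalation is for subjects without improvement, and the share who escalate is not given.

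It can also be argued that the efficacy interim is the sponsor's choice, and that it would be enough to state what stopping means.

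These points limit the finding to the case where a stop is taken, but the conflict remains. The 30% sentence follows directly on the stopping decision and is the only criterion offered for it, so an efficacy stop is permitted on a fair reading. Defining the consequences would cure the ambiguity but would still allow a stop that misses the target and has no control group to protect.

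**Conclusion.** The concern holds conditionally. Section 7.2 permits an efficacy stop on 12-week data from five subjects and does not define what stopping means for those enrolled. If a stop were taken, the target of ten completers would be missed. Spinal cord fractional anisotropy, echocardiogram and ECG, together with the week-24 part of FARS, cardiac MRI and the heart-failure biomarkers, would rest on fewer subjects.

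The size depends on what stopping means. With 6 followed to week 24, power at 1 SD falls from 80% to 51%, the CI half-width widens from 0.72 to 1.05 SD, and the upper limit for an unseen adverse event rises from 31% to 46%. If follow-up also ends, about 3 subjects have week-24 data, and fewer with faster accrual.

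The counts of 6 and 3 assume even accrual over 18 to 24 months without dropout. The power figures carry the plan's effect size of 1 SD, set for BNP, over to the other continuous measures.

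**What to change.** Amend the interim paragraph of Section 7.2 so that the 12-week look at five subjects is descriptive, with no efficacy stop and no efficacy conclusion. Delete the sentences that tie stopping to clinical significance and to a 3-month improvement. State that enrolment and week-24 assessments continue to the Section 4.5 target, with the existing Section 8.4 halting rule unchanged.

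If the sponsor does want an efficacy stop, the section should at least say what triggers it, whether enrolled subjects are still assessed at week 24, and how the week-24 endpoints and the ten-completer target are then handled.

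The amendment is to wording only. Its downside is that an apparently large benefit at 12 weeks would not shorten the trial: the roughly 10 − 6 = 4 remaining planned subjects would still be enrolled and followed.
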